3.2 Secondary outcomes

We are also aiming to evaluate if FMT can possibly alter gut permeability through urinalysis and peripheral blood DNA bacteria. We also aim to evaluate treatment safety using the Expanded Disability Status Scale (EDSS) and MRI as surrogates for any paradoxical worsening in MS disease activity. We are monitoring adverse events to assess tolerability.

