4. STUDY DESIGN

The proposed randomized, open label, with treat as usual control group, crossover phase II study will be conducted in 40 patients (n=20 per group) with the relapsing forms of multiple sclerosis according to the McDonald 2010 Criteria (Pollman 2011).

Patients will be randomized into 2 intervention groups. One will receive the FMT from baseline and for the first 6 months (early intervention group). On the other hand, the other group will be a control group during the first 6 months and will receive the FMT for the last 6 months of the study (Figure 1). The schedule of study procedures and evaluations for both groups is given in Tables 1 and 2. Patients will be screened for eligibility based on MS diagnosis and EDSS and if eligible then consented. All qualified patients will not be currently or recently treated with high dose steroids.

[figure not shown]

Figure 1. Study Design

At Visit 1, before FMT, patients will be evaluated for their vital signs, medical history and concomitant medications. Also before transplantation, patient's stool will be collected to study their microbial profile, blood analysis to evaluate cytokines levels as well as blood DNA bacteria and finally, urinalysis to assess gut permeability (baseline).

Stool samples for all microbiome analysis will be collected in the form of a used toilet paper packed in a black pouch and transferred in ambient conditions to the laboratory at the Lawson Health Research Institute at St. Joseph's Hospital and stored at -80 °C until the time of DNA extraction.

Peripheral blood will also be collected by standard technique venipuncture by a venipuncture certified and experienced RN. Cytokines levels will be assessed by Luminex in the Department of Microbiology and Immunology at the University of Western Ontario and blood DNA bacteria will be evaluated in St. Joseph Microbiology Laboratory.

For gut permeability patients will be instructed to drink lactulose solution and collect the urine throughout the night and first thing in the morning. A proper collecting bottle will be provided. Once the urine sample bottle reaches the laboratory at St. Joseph's Hospital, London, Ontario the total volume will be measured and an aliquot of 30ml total, 10mL in each sterile urine container (no other additives) will be separated and stored at -20C and sent on dry ice to [name] laboratory at Calgary, Alberta. All biological material will be transported according to biosafety regulations.

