6.2.1 Screening, Enrolment and Baseline

An informed consent form must be signed prior to initiating any procedures or evaluations for the purpose of the study (**Appendix B**). After the informed consent form has been signed patients will be randomized to receive FMT for the first 6 months of the study or to be a standard per treatment control group that will received treatment at the last 6 months of the study.

The following evaluations at baseline visit and prior to FMT will be performed in both groups:

- Medical history;
- Vital signs (including pulse, respiration rate, blood pressure and temperature);
- Physical Exam (including weight in kg);
- Concomitant medications;
- Dietary history;

- Expanded Disability Status Score (EDSS);
- Blood samples will be taken for haematology (including haemoglobin, red blood cell count, white blood cell count, differential and platelets);
- Blood samples will be taken for serum chemistry (sodium, potassium, chloride, uric acid, creatinine, blood urea nitrogen, total protein, calcium, albumin, total bilirubin, AST, ALT, alkaline phosphatase, glucose);
- Blood sample for multiplex cytokine profiling (includes pro-inflammatory (IL-6, IL-15, IL-17, GM-CSF, TNF α) and anti-inflammatory (IL-4, IL-10 and IL-14) cytokines).
- Clean catch, mid-stream urine for urinalysis and micro analysis (including pH, protein, glucose, ketones, nitrites, leukocyte esterase, RBCs, WBCs) and gut permeability;
- Blood sample for blood bacterial DNA
- Head MRI as baseline

After evaluation, the FMT via rectal enema will be performed by a RN in each visit.

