6.2.6 Urine analysis for gut permeability

Patients will be instructed not to consume alcohol on the day of the test or 5 days previously. Also, to eat supper before 6:00 pm, and then no food or drink is to be consumed after this time. At bedtime, patients will be advised to empty bladder and discard urine.

A packet containing sugar (lactulose) and mannitol will be provided. Patients will be instructed to empty the packet into a glass of water according to the table below.

Weight	Lactulose	Mannitol	Sucrose	Tap water
45kg-up	5 grams	2.0 grams	100 grams	450ml

Throughout the night and first thing in the morning, all urine must be collected and brought to St Joseph’s Health Care.

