7.0 ASSESSMENT OF EFFICACY

As this study is an immunological study, the following efficacy outcomes will be evaluated:

- Changes in peripheral blood cytokines within RMS patients between baseline and months 1 to 12 inclusive, for both groups. Luminex kit will be used.
- Changes on microbiome after FMT by analyzing the gut bacterial composition through stool analysis and blood bacteria DNA at baseline, and months 1 to 12 inclusive for both groups.
- Gut permeability through urine analysis at baseline, 6 and 12 months for both groups.

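### Section 6.2.1 assigns the baseline gut-permeability test to a mid-stream urine sample, contradicting the overnight collection in Sections 4 and 6.2.6; the sugars also differ and the analysed quantity is not named

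*Combined protocol and SAP*

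**What the plan says.** Section 3.2 makes gut permeability a secondary aim: to "evaluate if FMT can possibly alter gut permeability through urinalysis and peripheral blood DNA bacteria". Section 7.0 lists it among the efficacy outcomes as "Gut permeability through urine analysis at baseline, 6 and 12 months for both groups".

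Two specimens are described. The baseline list in Section 6.2.1 has an item that opens "Clean catch, mid-stream urine for urinalysis and micro analysis" and closes "leukocyte esterase, RBCs, WBCs) and gut permeability". Section 4 says "For gut permeability patients will be instructed to drink lactulose solution and collect the urine throughout the night and first thing in the morning", and adds that at the laboratory "the total volume will be measured and an aliquot of 30ml total" is set aside. Section 6.2.6, the dedicated procedure, says "Throughout the night and first thing in the morning, all urine must be collected".

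Three sets of sugars are named. Section 4 mentions lactulose. The text of Section 6.2.6 says "A packet containing sugar (lactulose) and mannitol will be provided". The table below that text has columns for lactulose, mannitol and sucrose.

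Section 9.3 gives a mixed-design ANOVA for biomarkers in general and defines no permeability variable.

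**The concern.** A mid-stream sample taken at the clinic is a different specimen from a complete overnight collection after a sugar drink. If staff work from the baseline list as written, the baseline value and the later values measure different things, and a change from baseline would mix a specimen effect with any effect of treatment.

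In the early group the error could not be repaired. Section 6.2.1 has FMT follow the baseline evaluations, while Section 6.2.6 requires preparation that starts days before the test and a collection through the night. An overnight collection missed before that visit cannot be replaced by another pre-treatment one, and Section 9.6 rules out imputation.

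Separately, while the sugars disagree and no quantity is named, the variable to be analysed could be settled after results are known, in an open-label trial.

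**Working it through.** The plan states no figure for this outcome, so the check sets the places side by side.

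| Place | Urine specimen for permeability | Sugars named | Visits |
|---|---|---|---|
| Section 6.2.1 | Mid-stream, shared with routine urinalysis | None | Baseline |
| Section 6.2.2 | Additional urine, type not given; the mid-stream item omits permeability | None | Baseline, 6, 12 |
| Section 4 | Overnight and first morning; total volume measured | Lactulose | Procedure not limited to a visit |
| Section 6.2.6, text | All overnight and first-morning urine | Lactulose, mannitol | Not limited to a visit |
| Section 6.2.6, table | Not applicable | Lactulose, mannitol, sucrose | Not limited to a visit |
| Tables 1 and 2 | Own row, separate from routine urinalysis; type not given | None | Baseline, 6, 12 |

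**Step 1: does the specimen matter?** Write C for the urinary concentration of a sugar, V for the urine volume and D for the amount taken.
- Recovery of one sugar = C × V / D. This needs the total volume, which a mid-stream sample does not give.
- Ratio of two recoveries from one specimen = (C1 × V / D1) / (C2 × V / D2) = (C1 / C2) × (D2 / D1). The volume cancels.

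Missing volume therefore defeats a recovery but not a ratio. What separates the specimens in either case is the collection window. The overnight urine accumulates excretion from bedtime to morning, whereas a mid-stream sample reflects part of a single void. The item in Section 6.2.1 also mentions no sugar drink.

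**Step 2: which contrasts would suffer?** Call the three planned values Y0, Y6 and Y12. If Y0 comes from a mid-stream sample and the others from overnight collections:
- Y6 − Y0 and Y12 − Y0 are not interpretable as change.
- Y12 − Y6 is unaffected.
- The comparison of Y6 between randomised groups is unaffected. Section 6.2.1 applies the same list to both groups, so its wording does not tie the fault to one arm. A poor baseline covariate would reduce the precision gained by adjustment, but would not bias that comparison.

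**Step 3: what could be analysed?** The sugar lists are nested. With k sugars there are k recoveries and k(k − 1)/2 pairwise ratios:
- lactulose alone: 1 + 0 = 1 quantity, and no ratio;
- lactulose and mannitol: 2 + 1 = 3;
- lactulose, mannitol and sucrose: 3 + 3 = 6.

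These are algebraic possibilities, and not all need be sensible. The documents select none of them and give no unit or direction of change.

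**The case against.** The strongest reply is that the phrase in Section 6.2.1 is loose drafting. Section 6.2.6 is the dedicated procedure and makes no exception for baseline. Section 4 describes the overnight collection without limiting it to a visit. Section 6.2.2 groups baseline with months 6 and 12 when it says urine is collected for permeability. Tables 1 and 2 give permeability urine a row apart from routine urinalysis. This stands: the overnight collection is probably intended at all three visits, and different specimens by visit are not a stated plan. It does not remove the fault, because Section 6.2.1 is an operative checklist, does not refer to Section 6.2.6, and concerns the visit that cannot be repeated before treatment in the early group. Section 3.2 and the Visit 1 description in Section 4 also call the permeability test urinalysis, which makes the misreading easier.

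On the sugars, the reply is that the lists are nested, that Section 4 only summarises, and that the text of Section 6.2.6 refers the patient to its table. This stands in part: a site following Section 6.2.6 would not give lactulose alone. The sentence describing the packet and the table still differ on sucrose, and Section 4 still differs from both.

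A reader might go further and infer that the secondary outcome is lost, or that a third of the measurements (40 patients × 3 visits = 120, of which 40 at baseline) are void. The documents do not support either. The first ignores the month 6 comparison. The second is a worst-case count that assumes every patient is handled by Section 6.2.1 against all the other sections.

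**Conclusion.** The contradiction is real and should be corrected. Followed literally, Section 6.2.1 yields a baseline that is not comparable with months 6 and 12 and spoils change from baseline for a stated secondary outcome. The exposure is one of three planned measurements per patient, and only where staff follow that item; the documents give no basis for estimating how often that would happen or how large the resulting error would be. The month 6 comparison between groups and the primary cytokine outcome are not affected.

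The disagreement over sugars and the unnamed quantity are separate from the specimen fault and would remain after it is corrected. Nothing in the documents settles which sugars, or which recovery or ratio, is right; that is for the sponsor.

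The conclusion assumes that Section 6.2.6 governs months 6 and 12, and that the month 6 collection in the late group is complete before its first FMT. An overnight collection brought to the visit implies the latter, but it is not stated for permeability urine.

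**What to change.** 1. In Section 6.2.1, delete the reference to gut permeability from the mid-stream item and add a separate item pointing to Section 6.2.6. Point Section 6.2.2 to the same place, so that one procedure covers baseline, month 6 and month 12.
2. Have the sponsor reconcile the sugars in Section 4, the text of Section 6.2.6 and its table.
3. State in advance, in Sections 7.0 and 9.3, the quantity to be analysed, as a recovery or a ratio that matches the reconciled test. If it is a recovery, put the measurement of total volume, now only in Section 4, into Section 6.2.6 as well.
4. Compare that quantity between the randomised groups at month 6, adjusted for baseline, and state that the month 6 collection is completed before the late group's first FMT.

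These are changes to the text. They add no visit, sample or patient, since the baseline and month 6 collections are already scheduled. They do have to pass through the amendment procedure in Section 10.1, and they should be in place before further baseline visits.

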6.2.2 Subsequent visits

On all subsequent visits, prior to FMT the following evaluations will be performed:

- Physical examination
- Rapid (urine) pregnancy test for women of childbearing potential;
- Vital signs (including pulse, respiration rate, blood pressure and temperature);
- Concomitant medications;
- EDSS;
- Blood samples will be taken for haematology (including haemoglobin, red blood cell count, white blood cell count, differential and platelets);
- Blood samples will be taken for serum chemistry (including: sodium, potassium, chloride, uric acid, creatinine, blood urea nitrogen, total protein, calcium, albumin, total bilirubin, AST, ALT, alkaline phosphatase, glucose);
- Clean catch, mid-stream urine for urinalysis and micro analysis (including pH, protein, glucose, ketones, nitrites, leukocyte esterase, RBCs, WBCs,);
- Blood sample for blood bacterial DNA
- Blood sample for multiplex cytokine profiling (includes pro-inflammatory (IL-6, IL-15, IL-17, GM-CSF, TNF α) and anti-inflammatory (IL-4, IL-10 and IL-14) cytokines).

After evaluation, the FMT via rectal enema will be performed by a RN in each visit.

At baseline, 6 and 12 months a head MRI will be performed. At these time points urine will be also collected to perform gut permeability analysis.

At any time during the study, if a patient has experienced an adverse event then they may be asked to return to the clinic for an unscheduled visit. Patients with adverse events will be followed to resolution.

6.2.3 Peripheral blood cytokines levels

Cytokine levels will be measured as previously described⁷². Peripheral blood will be collected into EDTA blood collection tubes ensuring complete mixing with anticoagulant to avoid clotting. Within 60 minutes of blood collection samples will be spun for 10 minutes at 4500xg. The plasma will be collected and aliquoted into cryovials. All samples will be collected and stored at -80°C before the plasma is measured for 25 immunological cytokines using a luminex-based multiplexed immunoassay. The Human Th17 Magnetic bead panel (HTH17MAG-14K, Millipore) will be used in this study to detect changes in Interleukin 1 β (IL-1 β), IL-2, IL-4, IL-5, IL-6, IL-9, IL-10, IL-12p70, IL-13, IL-15, IL-17A, IL-17E/IL-25, IL-17F, IL-21, IL-22, IL-23, IL-27, IL-28A, IL-31, IL-33, granulocyte macrophage colony stimulating factor (GM-CSF), interferon γ (IFN γ), macrophage inflammatory protein 3 α (MIP-3 α), tumour necrosis factor α (TNF α) and TNF β . Plasma samples will be run in duplicate and assays will be standardized as per product specifications. Plasma cytokine levels in healthy controls will be compared to levels in MS patients at all time points. Moreover, cytokine levels of MS patients at baseline (D0) will be compared to levels at 12 months to determine whether intervention (FMT) had an effect on pro- and anti-inflammatory cytokine levels.

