- To evaluate the safety of FMT in MS patients
- To evaluate tolerability of FMT in MS patients

Trial Design:

The proposed randomized, open label, controlled [treatment as usual control group], crossover study will be conducted in 40 patients (n=20 per group) diagnosed with the relapsing forms of multiple sclerosis according to the McDonald 2010 Criteria¹.

Based on the diagnostic criteria patients will be further screened to confirm eligibility and if eligible then consented.

Patients will be randomized 1:1 into two groups. One group will receive FMT, done by rectal enema administered by a RN, at baseline, month 1, month 2, month 3, month 4, and month 5 (early intervention group). The other group will receive treatment as per standard of care (treatment as usual control group) in the beginning of the study. For the last 6 months they will also receive FMT at month 6, month 7, month 8, month 9, month 10, and month 11 (late intervention group).

Clinical visits for both groups will be performed at baseline, and months 1 to 12 inclusive. During these visits a physical exam with vital signs, including a standardized neurological assessment Expanded Disability Status Scale – EDSS) will be done.

Patient's stools will be collected before each FMT procedure in both groups to evaluate gut microbial composition.

Urine will be collected to evaluate gut permeability at baseline, 6 and 12 months for both groups.

Peripheral blood samples also will be collected to evaluate circulating cytokine levels (IL-1 β , IL-2, IL-4, IL-5, IL-6, IL-9, IL-10, IL-12p70, IL-13, IL- 15, IL-17A, IL-17E/IL-25, IL-17F, IL-21, IL-22, IL-23, IL-27, IL-28A, IL-31, IL-33, GM-CSF, IFN γ , MIP-3 α , TNF α and TNF β) at baseline, months 1 to 12 inclusive for both groups.

Peripheral blood samples will also be collected to evaluate blood DNA bacteria at baseline, and months 1 to 12 inclusive for both groups.

Brain MRI with gadolinium [3T MRI machine at Robarts Research Institute] will be performed at baseline, 6 and 12 months for both groups as a safety biomarker [to rule out paradoxical effects; i.e. significant increase in MS activity as defined by Cutter's rule: 5 or more newly enhancing white matter lesions in the brain compared to the previous scan].

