Patients will also undergo a contrast-enhanced brain MRI scan at Robarts Institute in London Ontario. Other baseline assessments (prior to the first dose of therapy) include an EDSS, pregnancy test (if applicable), and physical exam. Blood samples are also taken at this visit in order to establish a baseline for routine chemistry/hematology. After all this assessments FMT will be performed by a trained nurse via a rectal enema

Patients will return to the clinic for visit 4 weeks after the first FMT. Another stool sample to evaluate the microbial before the second FMT will be collected. Also peripheral blood samples for cytokines and blood bacterial DNA analysis. This same routine procedure will be

repeated at month 2, 3, 4 and 5 for the early intervention group and at month 6, 7, 8, 9, 10 and 11 for the late intervention group. Both groups will come to clinic at baseline and month 1 to 12 inclusive, even if they are not receiving FMT. During all visits, a stool sample, a cytokine sample and a blood DNA bacteria sample will be collected. It is worth mentioning that at 6 and 12 months another urine analysis will be done to evaluate gut permeability and MRI study at Robarts Institute, London, Ontario for safety assessment will be performed for both groups.

Another safety assessment in each visit after FMT is to review of any adverse events that may have occurred. All patients receiving at least 1 week of treatment will be eligible for analysis.

Table 1. Early Intervention Group Schedule

[figure not shown]
Study Months	Pre-Visit	Baseline	Month 1	Month 2	Month 3	Month 4	Month 5	Month 6	Month 7	Month 8	Month 9	Month 10	Month 11	Month 12
Visit Duration	1.5hours	1.5hours	1.5hours	1.5hours	1.5hours	1.5hours	1.5hours	45min	45min	45min	45min	45min	45min	45min
Informed Consent Form	X													
Fecal Transplantation		X	X	X	X	X	X							
Height		X												
Weight, Vital Signs		X	X	X	X	X	X	X	X	X	X	X	X	X
Stool Sample		X	X	X	X	X	X	X	X	X	X	X	X	X
Urine: Gut Permeability		X						X						X
Circulating Cytokine Levels and Blood DNA		X	X	X	X	X	X	X	X	X	X	X	X	X
MRI		X						X						X
Routine Hematology and Urinalysis		X	X	X	X	X	X	X	X	X	X	X	X	X
Physical Exam/ EDSS		X	X	X	X	X	X	X	X	X	X	X	X	X

Table 2. Late Intervention Group Schedule

Study Months	Pre-Visit	Baseline	Month 1	Month 2	Month 3	Month 4	Month 5	Month 6	Month 7	Month 8	Month 9	Month 10	Month 11	Month 12

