9.3 Biomarkers

We will analyze mean differences between two independent groups whilst subjecting participants to repeated measures overtime to assess variability between- and within-subjects variable. Therefore, we will use the mixed-design ANOVA model.

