9.7 Evaluable Patients

All patients who received 1 week of study treatment will be included in all analyses and listings.

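### Section 6.2.3 judges the FMT effect from the baseline-to-month-12 cytokine change, when no untreated group remains, and section 9.3 names no controlled contrast to decide instead

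*Combined protocol and SAP*

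**What the plan says.** The Clinical Study Synopsis (Trial Design) gives the early group its FMTs "at baseline, month 1, month 2, month 3, month 4, and month 5 (early intervention group"). For the late group it says "For the last 6 months they will also receive FMT at month 6, month 7, month 8, month 9, month 10, and month 11". Tables 1 and 2 in section 4 agree. Section 6.2.2 places the assessments, including the cytokine sample, before the FMT of the same visit: "On all subsequent visits, prior to FMT the following evaluations will be performed".

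Three places bear on how cytokines will be analysed:

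- Section 6.2.3 says that "cytokine levels of MS patients at baseline (D0) will be compared to levels at 12 months to determine whether intervention (FMT) had an effect". It does not mention group.
- Section 7.0 lists as the outcome "Changes in peripheral blood cytokines within RMS patients between baseline and months 1 to 12 inclusive, for both groups".
- Section 9.3 says "We will analyze mean differences between two independent groups whilst subjecting participants to repeated measures overtime", using a mixed-design ANOVA. It names no term, window or contrast.

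On who is analysed, section 9.7 says "All patients who received 1 week of study treatment will be included in all analyses and listings". Section 4 says "All patients receiving at least 1 week of treatment will be eligible for analysis", and the synopsis has a near-identical sentence. Section 9.6 rules out imputation.

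**The concern.** The primary outcome (section 3.1) is whether FMT changes the cytokine profile. The sentence in 6.2.3 that ties a specific comparison to that question uses a visit at which nobody is untreated. The randomised treatment-as-usual group, the design's main strength, plays no part in it. Anything that moves cytokines in both groups over a year would be credited to FMT. One candidate is disease-modifying therapy, which is permitted (synopsis exclusion criterion 3; section 2.6) and which the plan does not hold constant.

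The comparison can also dilute a real effect. Section 6.2.5 treats as open how long recipients take to revert to their original microbiota. At month 12 the early group is seven months past its last FMT and the late group one month.

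The study is exploratory (section 9.1), so what is at stake is a false or weakened lead for later work.

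**Working it through.** **Plan's own figure.** There is none to reproduce. Section 6.3 gives a type I error of 0.05 and power of 0.8 but derives no sample size, and section 9.1 calls the number arbitrary. The documents give no drift, SD, within-patient correlation or dropout rate, so those inputs below are assumptions. Tests are taken as two-sided, and all figures are for one cytokine.

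**Step 1: exposure at each sample.** Count the FMTs given at visits earlier than the sample (early: visits 0-5; late: visits 6-11).

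| Sample | Early | Late |
|---|---|---|
| Month 6 | 6 | 0 |
| Month 12 | 6 | 6 |

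Time since last FMT at month 12: 12 − 5 = 7 months (early) and 12 − 11 = 1 month (late).

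**Step 2: what each comparison estimates.** Let the effect be d while treated and p·d after stopping.

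- Early minus late at month 6: d, whatever p is.
- Early minus late at month 12: (p − 1)d, so −d, −0.5d or 0 for p = 0, 0.5 or 1.
- Pooled change at month 12: (p + 1)d/2 plus drift. If the effect has gone in the early group, this is d/2 plus drift.
- Group main effect over 13 visits: [6 + 6(p − 1)]d/13 = 6p·d/13, so 0, 0.23d or 0.46d.

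The plan does not nominate the last of these. It shows only that the choice of term within the ANOVA matters.

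**Step 3: false attribution.** Assume no FMT effect and a common drift δ, in SDs of the change. The paired t-test has noncentrality δ√n.

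| δ | n = 40: δ√n | rejects | n = 20: δ√n | rejects |
|---|---|---|---|---|
| 0.1 | 0.632 | 0.095 | 0.447 | 0.071 |
| 0.2 | 1.265 | 0.235 | 0.894 | 0.136 |
| 0.3 | 1.897 | 0.457 | 1.342 | 0.247 |

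In simulation under the same null and a linear common drift (20 per group, 13 visits, 6,000 trials per case), an early-versus-late ANCOVA over months 1-6 rejects in 4.8% to 5.6%.

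**Step 4: what a controlled contrast can detect.** The inputs are 20 per group, unit SD, 80% power and ANCOVA on baseline with 40 − 3 = 37 df. Residual variance = Var(outcome) − Cov(outcome, baseline)². For the months 1-6 average under equal correlation r this is (1 + 5r)/6 − r². At r = 0.5 it is 0.583 − 0.25 = 0.333 (SD 0.577), which gives 0.525 SD detectable.

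| Correlation | Months 1-6 average, constant effect | Same, final effect if linear build-up (÷ 3.5/6) | Month 6 alone |
|---|---|---|---|
| Equal 0.3 | 0.520 | 0.891 | 0.868 |
| Equal 0.5 | 0.525 | 0.900 | 0.788 |
| Equal 0.7 | 0.464 | 0.795 | 0.650 |
| AR(1) 0.5 | 0.549 | 0.941 | 0.910 |
| AR(1) 0.7 | 0.607 | 1.041 | 0.903 |
| AR(1) 0.9 | 0.523 | 0.896 | 0.771 |

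Analysing the months 1-6 average as a plain change score, without ANCOVA, raises the first column to between 0.54 and 0.94 SD.

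**Step 5: the inclusion rule.** Section 2.2 uses the term study treatment for what the enema delivers. A late-group patient who leaves before month 6 has had none. An early-group patient who leaves in the same window, after a week, has had some. If a share q leaves each group by month 6 and leavers differ by s SD, the bias in the early-minus-late contrast is about q × s:

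- q = 5%: 0.05 × 0.5 = 0.025 to 0.05 × 1 = 0.05 SD
- q = 10%: 0.10 × 0.5 = 0.05 to 0.10 × 1 = 0.10 SD

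Simulated rejection with 2 of 20 lost per group and no FMT effect is 5.0% to 6.2%, close to nominal.

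**The case against.** **Section 9.3 already provides a controlled analysis.** Section 6.2.3 is a laboratory-methods section. Section 3 describes a controlled trial, and 9.3 plans a comparison of two independent groups over time. A mixed-design ANOVA would ordinarily give a group-by-time test that draws on the untreated months. This stands in part: a reader might infer that no between-group analysis is planned, and the documents do not support that. What remains is that 9.3 does not say which term or window decides, and that 6.2.3 points to a different comparison.

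**Drift is assumed.** This is correct. The rates in step 3 illustrate a vulnerability and do not estimate what will happen. Concomitant medications are reviewed at every visit (6.2.1, 6.2.2), so therapy changes can be seen, although 9.3 names no adjustment for them.

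**The inclusion rule may do little harm.** This largely stands.

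- The synopsis and section 4 say only treatment, and speak of eligibility for analysis. Since the synopsis also describes the control group as receiving standard-of-care treatment, those sentences need not exclude anyone.
- With no imputation, a complete-case ANOVA would lose early-group leavers too, and the imbalance might not arise.
- The 90% target in section 5.4 covers progression to FMT and all follow-up. It is not a dropout rate for months 1-6.

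**No single contrast is best.** This is also fair. For a purely transient 0.5 SD effect, simulated power is 87% to over 99% for the interaction, against 63% to 75% for the months 1-6 ANCOVA. For a persistent effect the interaction falls to 30% to 69%, while the ANCOVA is unchanged. Under linear build-up, month 6 alone does better than the average in all six correlation structures.

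**Conclusion.** The point holds in a limited form. The month-12 comparison in 6.2.3 cannot support a conclusion about FMT, because the schedule leaves no untreated group by then; this needs no assumption. The size of the error does: 9.5% to 45.7% false rejection (pooled, n = 40) rests on an assumed drift of 0.1 to 0.3 SD of the change. Section 9.3 can use the control group but leaves the deciding test open, across 25 cytokines and 13 visits.

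The 9.7 issue is secondary. A reader might infer a serious selection bias, but the documents give no dropout rate. Over the assumed range the bias is about 0.03 to 0.10 SD, and it may vanish in a complete-case analysis.

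For an exploratory study of convenience size, this should be fixed but does not invalidate the design.

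**What to change.** 1. **Section 6.2.3.** Report the baseline-to-month-12 change descriptively by group, without attributing it to FMT.
2. **Section 9.3.** Before any cytokine data are seen, name one early-versus-late contrast confined to the period when the late group is untreated, analysed by ANCOVA on the baseline value. Two reasonable choices are the months 1-6 average (0.46 to 0.61 SD detectable if the effect is constant from month 1) and month 6 alone (0.65 to 0.91 SD, preferable if the effect builds linearly). State that the late group's month-6 sample counts as control because it precedes that group's first FMT. Keep group-by-time and months 7-12 as supportive.
3. **Section 9.7, and the related sentences in the synopsis and section 4.** For this contrast, include all randomised patients, as assigned, who have a baseline and at least one cytokine sample in the window.

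The cost is wording; no visits or samples are added. The statistical price is a 20-versus-20 comparison, per single cytokine of 25 and before any multiplicity adjustment, with less power than the interaction if the effect is purely transient. If the average is chosen, using partial data also dilutes a building effect slightly. With 4 of 20 early-group patients seen for only 1 to 5 months, the group average falls from 3.5/6 = 0.583 to 0.8 × 0.583 + 0.2 × 0.333 = 0.533 of the final effect.
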